### **6.9.2 Concomitant Medications**

Other than the prohibited medications listed in [Section 6.9.1](#), treatment with the following medications as outlined in this section is permitted during the study.

During Period C, the safety Follow-up Period, all concomitant medications may be continued without the restrictions mentioned below per the discretion of the Investigator.

#### **Oral Antibiotic Therapy**

Participants may use oral antibiotic therapy for the treatment of HS provided the dosing regimen (dose and frequency) has been stable for at least 4 consecutive weeks (28 days) prior to Baseline and throughout the duration of the 28-week Treatment Period of the trial. Antibiotics taken on a PRN basis are not considered a stable dose. Permitted oral concomitant antibiotics are the following: oral doxycycline (at a dose of up to 100 mg PO BID) or minocycline (at a dose of up to 100 mg PO BID). If oral antibiotic therapy is used concomitantly, the dose should remain stable and constant.

#### **Analgesic Therapy for HS-Related Pain and Non-HS-Related Pain**

Most participants will be required to washout all analgesics prior to Baseline. For more guidance, refer to [Table 4](#). This includes analgesics for HS-related and non-HS-related pain. However, if a participant is on a stable dose of ibuprofen or acetaminophen (PRN is not considered stable) for HS-related pain, the participant may continue the analgesic, provided the dose is stable for

10 days prior to Baseline and is anticipated to remain stable through Week 28. Additionally, if a participant is on a stable dose of non-opioid analgesic (other than ibuprofen or acetaminophen) for non-HS-related pain (eg, gabapentin for osteoarthritis), the participant may continue the analgesic, provided the dose is stable for 14 days prior to Baseline and is anticipated to remain stable through Week 28.

If a participant experiences HS-related or non-HS-related pain after Baseline, they may initiate analgesic treatment. Analgesic therapy is limited to ibuprofen (at a dose of up to 800 mg PO every 6 hours not to exceed 3.2 gm/24 hours) and/or acetaminophen (at a dose of up to 1000 mg PO every 6 hours not to exceed 4.0 gm/24 hours or a lower maximum dose as per local regulations). Participants in Australia may receive tramadol (at a dose of up to 100 mg PO every 4 hours, not to exceed 400 mg/24 hours) as a rescue therapy after Baseline for HS-related pain that is refractory to treatment with ibuprofen or acetaminophen per Investigator discretion. Participants will complete a daily diary of their analgesic use. Participants will be required to record their analgesic use daily through Week 28. Any changes in dosing and/or frequency need to be reported in the daily diary; documentation of only PRN use is not permitted. Dose adjustments of ibuprofen or acetaminophen up to the maximum permitted dose and frequency are allowed during the study.

### **Lesion Intervention**

In the event that an acutely painful lesion occurs that requires an immediate intervention, Investigators will have the option to perform protocol-allowed interventions.

Only 2 types of interventions are allowed: injection with intralesional triamcinolone acetonide suspension (at a concentration of up to 10 mg/mL, up to 1 mL) and I&D.

For participants in Chile, intralesional betamethasone (at a maximum dose of up to 1.5 mg, diluted in sterile normal saline per Investigator discretion) may be substituted for intralesional triamcinolone.

New systemic and topical therapies following I&D (including antibiotics), are prohibited.

Participants should continue using any ongoing oral and topical therapies (with the constraints as described in [Section 6.9.1](#)) during the study. Concomitant medications associated with the lesion intervention(s) must be captured in the source and on the appropriate eCRF.

Protocol-allowed interventions are prohibited during Period A for all participants except those in Australia. For participants in Australia, 2 lesion interventions are allowed during Period A. An intervention can occur on two different lesions at the same visit or on the same lesion at two different study visits.

During Period B, maximally two interventions every 4 weeks are permitted. An intervention can occur on two different lesions at the same visit or on the same lesion at two different study visits.

All study visit assessments must occur before any interventions are performed. The site will be required to count any lesion that undergoes an intervention as permanently present from the date of the intervention and must account for it in the source document(s) and on the appropriate eCRF.

## **Antiseptic Therapy**

Participants may use 1 of the following over-the-counter topical antiseptics on their HS lesions: chlorhexidine gluconate, triclosan, benzoyl peroxide, dilute bleach in bathwater, or zinc pyrithione shampoo as body wash. However, they must use it 2 weeks prior to Baseline Visit and throughout the duration of the 28-week Treatment Period of the trial.

## **Wound Care**

Concomitant use of wound care dressings on HS wounds is allowed; however, options are limited to alginates, hydrocolloids, and hydrogels.

## **Local Anesthetic**

Local anesthetic (with lidocaine or lidocaine with epinephrine, dose per Investigator discretion) is permitted in the setting of (1) rescue treatment with intralesional triamcinolone acetonide via intradermal injection, (2) rescue treatment with local I&D, and (3) [REDACTED] assessment.

## 7 DISCONTINUATION OF STUDY INTERVENTION AND PARTICIPANT DISCONTINUATION/WITHDRAWAL

Discontinuation of specific sites or of the study as a whole are detailed in Appendix 1 ([Section 10.1](#)).

### 7.1 DISCONTINUATION OF STUDY INTERVENTION

#### 7.1.1 Permanent discontinuation

It may be necessary for a participant to permanently discontinue study intervention. If study intervention is permanently discontinued, the participant should, if at all possible, remain in the study to be evaluated for all assessments indicated in the SoA. See the SoA for data to be collected at the time of discontinuation of study intervention and follow-up and for any further evaluations that need to be completed.

Under the following circumstances IMP should be permanently discontinued:

- At participant's own request or at the request of their LAR (ie, an individual or judicial or other body authorized under applicable law to consent on behalf of a prospective participant to the participant's participation in the procedure(s) involved in the research).
- If, in the Investigator's opinion, continuation in the study would be detrimental to the participant's well-being.
- At the specific request of the Sponsor.
- In the event of a protocol deviation, at the discretion of the Investigator or the Sponsor.
- Severe allergic or hypersensitivity reaction (See [Section 10.6](#)).
- Confirmed diagnosis of malignancy.
- Major surgery or elective surgical procedure.
- Severe intercurrent illness.
- Pregnancy (See [Section 8.4.5](#)).
- Any opportunistic infection, such as TB or other infections whose nature or course may suggest an immunocompromised status (See [Section 10.6](#)).
- Severe laboratory abnormalities:
  - Neutrophil count  $<1\ 500/\text{mm}^3$  (See [Section 10.6](#)).
  - Platelet count  $<100\ 000/\text{mm}^3$  (See [Section 10.6](#)).
  - ALT  $>5\ \text{ULN}$  or ALT  $>3\ \text{ULN}$  with concomitant total bilirubin  $>2\ \text{ULN}$  (unless participant with documented Gilbert's syndrome) (See [Section 10.6](#)).
  - Increase in serum creatinine as per algorithm in [Section 10.6](#).
- Any clinically significant abnormal laboratory value will be immediately rechecked for confirmation after 24 hours before making a decision of permanent discontinuation of the IMP for the concerned participant. If the laboratory abnormality is considered causally related to the IMP, the IMP will be permanently discontinued. In cases where a causal

relationship to the IMP can be reasonably excluded (ie, an alternative cause is evident), the IMP will be discontinued but it may be resumed when the laboratory abnormality is sufficiently normalized. A decision to resume the IMP will be made jointly by the Investigator and Medical Monitor (Medical Monitor's written approval is required).

- Occurrence of AEs, that, in the opinion of Investigator/Sponsor, may jeopardize participant's safety or data integrity.
- Initiation of systemic immunosuppressive or immunomodulating drugs such as those described in [Section 6.9.1](#).
- Receipt of a live (attenuated) immunization.
- Treatment with any prohibited systemic concomitant medication or procedure (See [Section 6.9.1](#)).
- Treatment with any prohibited rescue medication or procedure (See [Section 6.9.1](#)).
- Missing >2 doses of scheduled IMP administration.

See the SoA ([Section 1.3](#)) for data to be collected at the time of definitive intervention discontinuation and follow-up and for any further evaluations that need to be completed. Any abnormal laboratory value or ECG parameter will be immediately rechecked for confirmation after 24 hours before making a decision of permanent discontinuation of the IMP for the concerned participant.

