#### **7.1.2 Liver chemistry stopping criteria**

Discontinuation of study intervention for abnormal liver tests is required by the Investigator when a participant meets one of the conditions outlined in [Section 10.6](#) or in the presence of abnormal liver chemistries not meeting protocol-specified stopping rules if the Investigator believes that it is in best interest of the participant.

Study intervention restart or rechallenge after liver chemistry stopping criteria are met by any participant in this study are not allowed.

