### 7.1.5 Rechallenge

Reinitiation of intervention with the IMP will be done under close and appropriate clinical and/or laboratory monitoring once the Investigator will have considered according to his/her best medical judgment that the responsibility of the IMP(s) in the occurrence of the concerned adverse event

was unlikely and if the selection criteria for the study are still met (refer to [Section 5.1](#) and [Section 5.2](#)).

For a regional or national emergency declared by a governmental agency, contingency measures are included in Appendix 9 ([Section 10.9](#): Contingency measures for a regional or national emergency that is declared by a governmental agency).

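### Protocol 7.1.1 and 7.1.2 give opposite instructions on restarting IMP when a liver stopping limit is met and another cause is evident

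*Protocol*

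**What the plan says.** Three parts of Protocol Section 7.1 bear on restart after a liver abnormality.

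- **7.1.1, Permanent discontinuation.** The list opens with "Under the following circumstances IMP should be permanently discontinued". Under severe laboratory abnormalities it includes ALT >5 ULN, or ALT >3 ULN with total bilirubin >2 ULN (documented Gilbert's syndrome excepted), with a pointer to Section 10.6. The next bullet begins "Any clinically significant abnormal laboratory value will be immediately rechecked for confirmation after 24 hours". It then splits by cause. If the abnormality is judged causally related to IMP, IMP stops permanently. If another cause is evident, "the IMP will be discontinued but it may be resumed when the laboratory abnormality is sufficiently normalized". Resumption is decided jointly by the Investigator and the Medical Monitor, and the latter must approve in writing. Liver tests are not excepted.
- **7.1.2, Liver chemistry stopping criteria.** Discontinuation is required when a condition in Section 10.6 is met. The section then says: "Study intervention restart or rechallenge after liver chemistry stopping criteria are met by any participant in this study are not allowed". An alternative cause is not excepted.
- **7.1.5, Rechallenge.** "Reinitiation of intervention with the IMP will be done under close and appropriate clinical and/or laboratory monitoring", provided that the Investigator judges IMP unlikely to be responsible for the event and the selection criteria are still met. Liver tests are not mentioned.

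Sections 6.2 and 7.1.1 also make missing more than 2 doses a reason for permanent discontinuation, which limits how long any interruption can last.

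**The concern.** Section 7.1.1 names the liver limits and, in the very next bullet, makes permanence depend on causality for any clinically significant laboratory value. Section 7.1.2 makes restart unavailable whatever the cause. An Investigator and a Medical Monitor who apply 7.1.1 as written could approve what 7.1.2 rules out. If they apply 7.1.2, they refuse what 7.1.1 allows them to consider.

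Re-exposure after a liver signal is at stake; Section 8.4.7 already makes ALT above 3 times ULN an event of special interest. Either decision could also be recorded as a deviation from the other section. Whether the stop is labelled permanent then determines how the participant appears in several safety and disposition summaries.

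**Working it through.** The plan gives no figure to reproduce. The check sets the rules side by side and applies them to one case.

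**1. Do the two rules share a trigger?** The 7.1.1 liver item and 7.1.2 both refer to Section 10.6. The ALT flow chart there is not shown, so identical thresholds cannot be confirmed. The overlap rests on the shared cross-reference.

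**2. Apply each rule to the same findings:** ALT at a stopping limit, alternative cause evident, value normalized, no more than 2 doses missed.

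| Rule | Result |
|---|---|
| 7.1.1, list entry | Permanent discontinuation |
| 7.1.1, next bullet | May be resumed, with written approval |
| 7.1.2 | No restart or rechallenge |
| 7.1.5 | Reinitiation possible if IMP is unlikely to be responsible and selection criteria are still met |

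The second and third rows are opposed. The first and second show that 7.1.1 is also not settled within itself.

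**3. Can the case arise within the missed-dose limit?** Dosing is every 2 weeks. Missing 2 consecutive doses leaves 3 × 2 = 6 weeks between administrations. A value could normalize within that time, so the limit narrows the conflict but does not remove it.

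**4. Does other visible text settle it?** No.
- A footnote to the 10.6 ALT chart makes an exception where a protocol-defined permanent-discontinuation criterion is met. That sends the reader back to the criteria in question.
- The visible ALT evaluation box covers work-up and monitoring after IMP is stopped, and gives no restart instruction.
- The note to Table 12 sends the reader to 7.1.2 and 10.6.

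**5. What changes in the analysis?**
- *Primary endpoint:* under Protocol 9.2.2.2 and SAP 2.2.2, discontinuation for reasons other than lack of efficacy follows treatment policy. Data after the stop are used whichever rule is applied.
- *Safety and disposition:* a permanent stop enters the table of adverse events leading to permanent intervention discontinuation (SAP Table 7) and the disposition counts (SAP 4.2). A resumed interruption does not.
- *Exposure and compliance (SAP 2.7.1), by illustration:* assume doses at Weeks 0, 2 and 4, with Weeks 6 and 8 missed.
  - No restart: exposure is 4 + 2 = 6 weeks and compliance is 3/3 = 100%.
  - Restart at Week 10, doses through Week 14, open-label start at Week 16: exposure is min(16, 14 + 2) = 16 weeks and compliance is 6/8 = 75%, below the SAP's 80% cut.

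The dose timing is assumed. It only shows how the classification feeds through.

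**The case against.** The strongest reply is that the text can be read coherently. The liver limits sit under a list headed as permanent. The resumption clause is a separate bullet, and could be meant for other clinically significant values. Section 7.1.2 is specific and categorical, and a specific prohibition is ordinarily taken to limit a general permission. The temporary-interruption examples in 7.1.4 name neutrophils, platelets and creatine phosphokinase, but no liver test.

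That reading is possible, but the supplied text does not state it. The clause covers any clinically significant laboratory value and follows directly after the named liver limits. The 7.1.4 list is given as examples. Nor does a place on the 7.1.1 list reliably mean permanent: 7.1.1 lists platelets <100 000/mm³, while 7.1.4 treats counts ≤100 × 10⁹/L but >50 × 10⁹/L (the same upper figure) as grounds for temporary interruption.

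Four parts of the reply stand and limit the point:
- Resumption is not a site decision. It needs the Medical Monitor's written approval, which limits divergence between sites, although the Medical Monitor has the same two rules.
- The missed-dose limit excludes longer interruptions.
- Section 7.1.5 is generic. It requires the selection criteria to be met, and these include an ALT limit (E 28). It adds an unqualified permission rather than a second liver-specific conflict.
- The 10.6 flow chart cannot be seen and might contain a restart instruction.

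**Conclusion.** The contradiction between 7.1.1 and 7.1.2 is real and should be corrected, because it concerns re-dosing after a liver signal. It applies to participants who meet a liver limit, have an evident alternative cause, normalize and have missed no more than 2 doses. It assumes that both sections mean the same Section 10.6 conditions, and that the chart not shown does not resolve the matter.

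A reader might infer more than the documents support:
- *That sites will treat like cases differently as a matter of course.* The written-approval requirement makes this a central decision, so inconsistency is possible but limited.
- *That every liver case with another cause is affected.* The normalization and missed-dose conditions exclude some.
- *That a rate can be given.* The documents provide none. One case among about 84 participants is 1/84 = 1.2%, which is the weight of a single participant and not a forecast.
- *That the primary result is at risk.* The intercurrent-event rule is the same under either reading. An individual's observed Week 16 status could differ with exposure, but the estimand and its handling do not change.

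The effect is on participant safety, consistent conduct and descriptive summaries.

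**What to change.** Reconcile 7.1.1, 7.1.2 and 7.1.5 so that one stated rule governs restart after the liver stopping criteria are met. State in 7.1.1 whether its resumption clause applies to the ALT and ALT-with-bilirubin limits, and cross-refer to the governing section from 7.1.5. Check the Section 10.6 ALT chart for any restart instruction and align it. Which rule to adopt is for the sponsor's clinical team; this review takes no position.

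The cost is one clarifying sentence with cross-references in the next amendment, and a letter to sites and the Medical Monitor. Sample size, data collection and the SAP's analyses need no change. Any participant already stopped at a liver limit should be checked, so that the permanent or temporary label in the database follows the rule adopted.

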### **Handling of participants after permanent intervention discontinuation**

Participants will be followed-up according to the study procedures specified in this protocol up to the scheduled date of study completion, or up to recovery or stabilization of any AE to be followed-up as specified in this protocol, whichever comes last.

If possible, and after the permanent discontinuation of intervention, the participants will be assessed using the procedure normally planned for the last dosing day with the IMP including a pharmacokinetics sample, if appropriate.

All cases of permanent intervention discontinuation must be recorded by the Investigator in the appropriate pages of the eCRF when considered as confirmed.

#### **7.1.2 Liver chemistry stopping criteria**

Discontinuation of study intervention for abnormal liver tests is required by the Investigator when a participant meets one of the conditions outlined in [Section 10.6](#) or in the presence of abnormal liver chemistries not meeting protocol-specified stopping rules if the Investigator believes that it is in best interest of the participant.

Study intervention restart or rechallenge after liver chemistry stopping criteria are met by any participant in this study are not allowed.

### 7.1.3 QTc stopping criteria

Administration of study drug should be interrupted if a participant meets either bulleted criterion:

- QTc >500 msec confirmed by repeat measurement or manual over-read.
- QTc increase from Baseline >60 msec.

If a clinically significant finding is identified (including, but not limited to changes from Baseline in QT interval corrected using formula (QTcF) after enrollment, the Investigator or qualified designee will determine if the participant can continue on the study intervention and if any change in participant management is needed). This review of the ECG printed at the time of collection must be documented. Any new clinically relevant finding should be reported as an AE.

### 7.1.4 Temporary discontinuation

Temporary intervention discontinuation decided by the Investigator corresponds to  $\leq 2$  doses not administered to the participant.

Dosing of IMP should be temporarily interrupted for the following reasons:

- Clinically important laboratory abnormalities, such as:
  - Absolute neutrophil count  $\leq 1.0 \times 10^9/L$  but  $> 0.5 \times 10^9/L$ ,
  - Platelet count  $\leq 100 \times 10^9/L$  but  $> 50 \times 10^9/L$ ,
  - Creatine phosphokinase  $> 10 \times$  ULN.
- Other intercurrent illness.
- An infection requiring systemic treatment with antibiotic, antifungal, antiviral, antiparasitic or antiprotozoal agents, or requiring oral treatment with such agents for more than 2 weeks.
- Where elective surgery is required, this must be communicated in writing with the Medical Monitor regarding temporary discontinuation of IMP prior to any planned surgical intervention. IMP **must not** be re-started without communication with the Medical Monitor.

Temporary intervention discontinuation may be considered by the Investigator because of suspected AEs or disruption of the clinical trial due to a regional or national emergency declared by a governmental agency (Appendix 9 [[Section 10.9: Contingency measures for a regional or national emergency that is declared by a governmental agency](#)]). For all temporary intervention discontinuations, duration should be recorded by the Investigator in the appropriate pages of the CRF or eCRF.

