- Positive antibody to hepatitis B surface antigen (anti-HBs) with positive HBV DNA PCR test or,
- Positive hepatitis C virus (HCV) antibody.

If a participant has a positive HBc Ab or anti-HBs followed by a negative HBV DNA PCR at screening and is subsequently randomized, they will undergo HBV DNA PCR testing every 3 months until the end of study visit.

If a participant has a positive HCV Ab and followed by a negative HCV ribonucleic acid (RNA) PCR at screening and is subsequently randomized, they will undergo HCV RNA PCR testing every 3 months until the end of study visit.

E 12. Elective surgery within 4 weeks prior to the Screening Visit or with planned surgery during the Treatment Period, or in the period up to 3 months following the last dose of IMP.

E 13. Positive COVID-19 molecular test, suspected of having COVID-19 infection, or known exposure to COVID-19 during the Screening Period.

E 14. History of COVID-19 infection within 4 weeks prior to Screening; history of mechanical ventilation or extracorporeal membrane oxygenation due to COVID-19 infection within 3 months prior to Screening or with residual significant complications from COVID-19 making it unsafe for the participant to enter this study.

E 15. Presence of active suicidal ideation, or positive suicide behavior, or participant has a lifetime history of suicide attempt (including an actual attempt, interrupted attempt, or aborted attempt), or participant has had suicidal ideation in the past 6 months as indicated

by a positive response (“Yes”) using the Screening or Baseline version of the Columbia-Suicide Severity Rating Scale (C-SSRS) or as assessed by the Investigator through participant interview and review of medical history.

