## Diagnostic assessments

E 27. Exclusion related to TB or nontuberculous mycobacteria (NTM) infection:

- Active or latent TB or NTM infection or a history of incompletely treated TB or NTM infection regardless of screening QuantiFERON TB gold test result.
- Participants with QuantiFERON TB gold test positive or 1 indeterminate test result (no active disease) are excluded from the study unless all of the following conditions are met:
  - Participants with a history of prior documented completed chemoprophylaxis for latent tuberculosis infection (TBI) (eg, acceptable treatments would be 9 months of isoniazid 300 mg PO daily or equivalent proven regimen per local guidelines) or treatment of active TBI who has obtained consultation with a specialist to rule out active TBI or treat active TBI.
  - Participants have written documentation for approval for participation in the present study approved by a TB specialist who ruled out latent or active TB infection or other mycobacterial infection in the participant.
- Clinically significant abnormality consistent with prior/active TB or NTM infection based upon chest radiograph with at least posterior-anterior view (radiograph must be taken within 12 weeks prior to Screening Visit or during the Screening Period). Additional lateral view is recommended but not required.
- Suspected extrapulmonary TB or NTM infection regardless of screening QuantiFERON TB gold test result.

- Participants at high risk of contracting TB, such as close contact with individuals with active or latent TB.
- Participant who received Bacille Calmette Guerin (BCG) vaccination within 12 months prior to Screening.

E 28. Any of the following laboratory abnormalities at the Screening Visit:

- Hemoglobin <10 g/dL.
- Absolute neutrophil count (ANC) <1500 /mm^3 (or <1000 /mm^3 for participants of African descent).
- Platelet count <100 000 /mm^3.
- Creatinine clearance <60 mL/min using Cockcroft-Gault equation.
- Alanine aminotransferase (ALT) or aspartate aminotransferase (AST) or alkaline phosphatase (ALP) >2 × ULN.
- Total Bilirubin >2 × ULN; unless the participant has been diagnosed with Gilbert disease documented by genetic testing.
- For participants in the EU: Fasting triglyceride level ≥500 mg/dL.

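### Elective surgery on treatment is a permanent stop in Protocol 7.1.1 but a temporary one in 7.1.4, and the text of 7.1.1 does not carry over the lower neutrophil limit that E 28 accepts at entry

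*Protocol*

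**What the plan says.** **Surgery.** Section 7.1.1 opens its list with "Under the following circumstances IMP should be permanently discontinued", and one entry is "Major surgery or elective surgical procedure". Section 7.1.4 lists reasons for temporary interruption, defined as no more than two doses not given. One of them is elective surgery: "Where elective surgery is required, this must be communicated in writing with the Medical Monitor regarding temporary discontinuation of IMP". It adds that drug may not be restarted without contact with the Medical Monitor. At entry, E 12 excludes "Elective surgery within 4 weeks prior to the Screening Visit or with planned surgery during the Treatment Period", and extends this to three months after the last dose.

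**Neutrophils.** Among the severe laboratory abnormalities, 7.1.1 lists a count below 1500/mm3 and refers to Section 10.6. E 28 uses the same limit at Screening but lowers it to 1000/mm3 "for participants of African descent".

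**Laboratory values in general.** Section 7.1.1 also says: "Any clinically significant abnormal laboratory value will be immediately rechecked for confirmation after 24 hours". If the abnormality is considered related to study drug, the stop is permanent. If a relationship can reasonably be excluded, "the IMP will be discontinued but it may be resumed when the laboratory abnormality is sufficiently normalized". Restarting in that case is for the site physician and the sponsor's monitor to settle together, and the latter must approve in writing. Section 7.1.4 has its own temporary bands: neutrophils above 0.5 and up to 1.0 x10^9/L, and platelets above 50 and up to 100 x10^9/L.

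**The concern.** A site that reads 7.1.1 first ends treatment for an elective operation. A site that reads 7.1.4 first pauses it and restarts. Both follow the protocol. The participant at the first site loses treatment that the other section would have allowed.

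The neutrophil limits raise a similar problem. A participant of African descent can be eligible with a count that the text of 7.1.1 calls a severe abnormality. If the count does not move, the stop can be met at the first post-Baseline blood count, with no drug effect at all. Section 2 reports US prevalence of hidradenitis suppurativa as 0.30% in African Americans and 0.09% in white individuals, and the US is a study country, so such participants can be expected. The documents do not say how many would have counts in the affected range.

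At stake are avoidable loss of treatment and uneven handling of stopping rules for an immunosuppressive agent.

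**Working it through.** No figure in the plan needs reproducing. The check sets the rules side by side and counts doses.

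**1. Surgery.** The same event appears in two lists with opposite consequences: permanent in 7.1.1, temporary in 7.1.4. The 7.1.4 restart condition would have no purpose if 7.1.1 always governed. E 12 removes surgery already planned at entry but does not cover a need that arises later. The surgery entry in 7.1.1 has no pointer to Section 10.6, so the missing charts are not where the answer would be expected.

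**2. Doses lost** (Table 6 and the schedule of activities: one dose every 2 weeks, Weeks 0 to 26).
- Planned doses: 26/2 + 1 = 14.
- Illustration: operation just before the Week 8 dose, in a participant who would otherwise complete treatment.
- Under 7.1.1: Weeks 8 to 26, (26 - 8)/2 + 1 = 10 doses lost.
- Under 7.1.4: at most 2 doses lost (Weeks 8 and 10). The gap between doses given is 3 x 2 = 6 weeks.
- Placebo participant stopped in Period A: the open-label doses at Weeks 16 to 26 are lost, (26 - 16)/2 + 1 = 6.
- US participant who would have been a Week 20 non-responder (last dose Week 18): the losses under 7.1.1 fall to (18 - 8)/2 + 1 = 6 doses in all, and to 2 open-label doses (Weeks 16 and 18) if on placebo.

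**3. Neutrophil limits.**
- E 28 floor for participants of African descent: 1000/mm3. Stop in 7.1.1: below 1500/mm3. Counts accepted at entry that also meet the stop: 1000-1499/mm3.
- Scheduled hematology with doses still to come: Weeks 4, 8, 12, 16, 20 and 24, so 6 counts (4 for a US Week 20 non-responder).
- The 24-hour recheck would only confirm this participant's usual value.
- The resume clause asks for sufficient normalization and gives no target for someone who entered below 1500. Section 7.1.5 tests restart against the selection criteria, which here means 1000/mm3.

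**4. Count bands in 7.1.4.** In common units, 1500/mm3 = 1.5 x10^9/L and 100 000/mm3 = 100 x10^9/L. The neutrophil band (0.5, 1.0] lies wholly below 1.5. The platelet band (50, 100] lies below 100 except at exactly 100. So 7.1.4 calls temporary a range that 7.1.1 lists for permanent discontinuation. The resume clause in 7.1.1 covers any clinically significant laboratory value, and 7.1.4 and 7.1.5 do not contradict it. The two can be applied together, and only a cross-reference is missing.

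**The case against.** **The neutrophil rule may already have its exception.** The entry in 7.1.1 refers to Section 10.6, whose neutropenia flowchart is not shown. A reader might infer that the stop has no exception at all. The documents do not support that. They support only that the text of 7.1.1 states none. This limit stands.

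**There is a plausible way back to treatment.** An unchanged pre-treatment count is a natural case for excluding a relationship to study drug. Section 8.3.4 accepts a return to Baseline as an end point for repeat testing, and 7.1.5 uses the selection criteria. This stands in part. The 8.3.4 sentence governs retesting rather than restart, and under the text of 7.1.1 drug is still stopped first and then needs a joint decision to resume.

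**The sections might seem to disagree on who approves restart after a low count.** They do not. Section 7.1.1 requires the Medical Monitor's written approval, and 7.1.4 and 7.1.5 are merely silent on approval for counts. Silence does not contradict a general requirement.

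**The event is uncommon and already supervised.** E 12 leaves only elective surgery not foreseen at entry, and 7.1.4 requires written contact with the Medical Monitor beforehand. That narrows the problem for sites that follow 7.1.4. It does nothing for a site that applies 7.1.1 and stops.

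**Conclusion.** The surgery conflict holds in full on the readable text and should be corrected. Its size for one affected participant is up to 10 doses lost rather than at most 2 in the Week 8 illustration, or all 6 open-label doses for a placebo participant stopped in Period A. These figures assume an otherwise complete treatment course.

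The neutrophil mismatch holds for the wording of 7.1.1 against E 28, over 1000-1499/mm3. It is conditional on what the Section 10.6 chart says. The overlap of count bands needs no more than a cross-reference.

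A reader might infer bias in the primary result. None is claimed: 7.1.1 asks that participants who stop stay under assessment if at all possible, and 9.2.2.2 uses data collected after discontinuation for reasons other than lack of efficacy. The documents give no rate for either event, so no number of affected participants is claimed.

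**What to change.** First check the Section 10.6 neutropenia chart. Then, in one amendment:

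1. **Surgery.** In 7.1.1, replace the entry with *Major surgery, whether elective or not*. Limit the 7.1.4 entry to *non-major elective surgery*, with restart only after the Medical Monitor agrees. The existing stop for more than two missed doses remains the limit on the interruption. Simply deleting the elective procedure from 7.1.1 would not be enough, because an operation that is both major and elective would still fall under both rules.
2. **Neutrophils, if 10.6 holds no exception.** Write the stop in 7.1.1 as *<1500/mm3, or <1000/mm3 for participants of African descent whose Baseline count was 1000-1499/mm3*. The link to Baseline matters. A limit of 1000 for every participant of African descent would remove the stop for someone who entered at a normal count and fell to 1100 on drug, and Table 1 says to stop drug if cytopenia occurs.
3. **Counts.** In 7.1.4, add a cross-reference to the recheck, causality and written-approval clause in 7.1.1.

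The cost is one protocol amendment with ethics approval under 10.1.1, plus health authority approval if it is classed as substantial. No new visits or tests are needed: the recheck, the scheduled counts and the Medical Monitor contact are already in the protocol.
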